A single center, non-randomized, controlled before-and-after clinical study was designed to examine the effects of inhaled dornase alfa in patients with acute respiratory distress syndrome secondary to COVID-19 pneumonia. A second standard of care patient population is to be collected as a case control group for comparison. After inclusion to the study and consent has been obtained, we will collect blood samples and perform diagnostic flexible bronchoscopy with bronchoalveolar lavage (BAL). Patients will then receive nebulized dornase alfa via vibrating mesh nebulizer through the ventilator circuit twice daily for 3 days. On day 4 after randomization, blood samples and BAL fluid samples will again be collected to determine change in serum and alveolar NET activity. Therapy will be discontinued in any patients who develop treatment failure defined as an increase in FiO₂ by 20%, reduction in static lung compliance by more than 10 or need for rescue therapies such as extracorporeal membrane oxygenation (ECMO) or inhaled nitric oxide. Primary outcome measure will be change in arterial oxygen saturation to inhaled fraction of oxygen (PaO₂/FiO₂) before and after therapy. Secondary outcomes to be included will be change in static lung compliance, duration of mechanical ventilation, length of ICU stay, length of hospitalization, secondary bacterial infections, and mortality.

Study Population and Data Collection

Patients are to be recruited from the medical intensive care unit at the University of Missouri, a 250-bed academic tertiary care medical center, after confirmation of ARDS secondary to SARS-CoV-2 infection and progression of care to requiring mechanical ventilation. Inclusion criteria included age \geq 18 years, hospitalized, and mechanically ventilated for illness related to SARS-CoV-2 infection, with individual or surrogate ability to sign informed consent, and negative urine-based pregnancy test in female patients. Exclusion criteria included contraindication or intolerance to dornase alfa, length of mechanical ventilation expected to be less than 48 hours, life expectancy less than 24 hours based upon judgment of treatment physician, pregnancy, or inability to obtain informed consent. For the first

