5 days and at day 14 if applicable, daily measurements of PaO₂/FiO₂, static lung compliance, and positive end expiratory pressure (PEEP) will be collected. Demographic and clinical data of the patients to be obtained from electronic medical records at enrollment. Clinical study information will include age, sex, co-morbidities, therapies received, serological testing, ventilator data, bacterial and viral culture data, days of hospitalization, days in the intensive care unit, days of mechanical ventilation and mortality.

Primary Statistical Plan and Analysis

The primary hypothesis for this study is that by giving an inhaled medication targeting alveolar NET formation there will be an improvement in alveolar gas exchange. A control group for comparison is added who will have received standard of care. Improvement in alveolar gas exchange will be defined as a change in PF ratio from baseline for both the treatment and control groups with comparison of 95% CI between groups. Secondary endpoints of change in static lung compliance and change in PEEP will be analyzed in a similar fashion to change in PF ratio. The study is not powered to determine additional secondary endpoints such as mortality and length of hospitalization, but values will be collected and analyzed as unpaired t-test with significant p-value < 0.05. Bronchoalveolar fluid analysis for MPO-DNA will be compared before and after therapy with paired t-test analysis with significant p-value < 0.05.

Potential Impact

Resources

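### The primary PF-ratio analysis names no estimate of the between-group difference, no success rule and no post-therapy day; one 95% CI for the difference in change at one named day would settle it

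*Combined protocol and SAP*

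**What the plan says.** The Research Design section words the outcome as a before-and-after measure: "Primary outcome measure will be change in arterial oxygen saturation to inhaled fraction of oxygen (PaO₂/FiO₂) before and after therapy". It names no day and does not mention controls at that point.

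The Primary Statistical Plan and Analysis section brings controls in ("A control group for comparison is added who will have received standard of care") and defines improvement as "change in PF ratio from baseline for both the treatment and control groups with comparison of 95% CI between groups". Nothing further is said about the estimate, model, test or criterion for success. Two other endpoints follow the same route: "Secondary endpoints of change in static lung compliance and change in PEEP will be analyzed in a similar fashion to change in PF ratio". For outcomes such as mortality and length of hospitalization, which the plan says it is not powered for, the same paragraph does give a direct between-group test: "values will be collected and analyzed as unpaired t-test with significant p-value < 0.05".

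On timing, dornase alfa is given for 3 days. The Study Population and Data Collection section schedules, for the first "5 days and at day 14 if applicable, daily measurements of" PF ratio, static compliance and PEEP. Day 4 appears only for sampling: "On day 4 after randomization, blood samples and BAL fluid samples will again be collected". That sentence counts days from randomization, although the design is described as non-randomized.

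**The concern.** The primary clause asks for a comparison of confidence intervals, which is not the same as a confidence interval for a comparison. At least three procedures fit the words:

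- **A.** The two groups' 95% CIs must not overlap.
- **B.** The treated group's CI lies above zero and the control group's CI includes zero.
- **C.** One 95% CI is computed for the difference in change.

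These have very different error rates, and the PF day is open as well. Whether the primary hypothesis is reported as supported could therefore turn on choices made after the data are seen. Under A the danger is a missed difference. Under B it is a false claim, because ventilated patients in both groups may improve over the same days for reasons unrelated to treatment.

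**Working it through.** The plan states no sample size, SD, allocation ratio, alpha or power for the primary, so it has no figure to reproduce. The only input taken from the plan is the 95% level. Everything else below is an assumption, labelled as such.

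**Reading A: non-overlap.** Let SE1 and SE2 be the standard errors of mean change in the two groups, and d the observed difference.

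- One CI for the difference excludes zero when |d| > 1.96 × √(SE1² + SE2²).
- Two separate CIs fail to overlap when |d| > 1.96 × (SE1 + SE2).
- In units of the standard error of the difference, the critical value under A is c = 1.96 × (SE1 + SE2)/√(SE1² + SE2²).
- Two-sided alpha is 2 × (1 − Φ(c)).
- An effect that the direct CI detects with an assumed 80% power lies at 1.960 + 0.842 = 2.802 standard errors. Power under A is then Φ(2.802 − c).

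| SE ratio (assumed) | c | c/1.96 | two-sided alpha | power under A |
|---|---|---|---|---|
| 1 | 2.772 | 1.414 | 0.0056 | 0.512 |
| 2 | 2.630 | 1.342 | 0.0085 | 0.568 |

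At equal SEs the observed difference must be 41% larger than the direct CI requires. About 29 points of power are lost (0.800 − 0.512 = 0.288). Recovering 80% power would need ((2.772 + 0.842)/2.802)² ≈ 1.66 times the sample size.

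A simulation with t-based CIs and equal SDs used 400,000 runs, with the effect set so that the pooled t-test has 80% power:

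| Treated/control (assumed) | power under A | direct CI above zero but the two CIs overlap |
|---|---|---|
| 10/10 | 0.448 | 0.351 |
| 20/20 | 0.483 | 0.317 |
| 30/30 | 0.493 | 0.308 |
| 10/20 | 0.469 | 0.331 |
| 10/40 | 0.498 | 0.302 |

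**Reading B: one CI above zero, the other including it.** Suppose both groups truly improve by the same m standard errors, with equal SEs. The chance of falsely favouring treatment is P(Z > 1.96 − m) × P(control CI includes zero).

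- m = 0: 0.025 × 0.95 = 0.024
- m = 1: 0.140
- m = 1.96: 0.5 × 0.5 = 0.250, the maximum
- m = 3: 0.127

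**Reading C: CI for the difference.** The critical value is 1.96 and two-sided alpha is 5%, for one fixed day.

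**Choice of day.** Suppose a direct 5% test (reading C) is used and either of two post-therapy days may be reported. With no true difference, the error is P(|Z1| > 1.96 or |Z2| > 1.96) for correlated normals. At assumed correlations of 0.5, 0.7 and 0.85 it is 0.0907, 0.0835 and 0.0746. The chance of falsely favouring treatment rises from 2.5% to 4.5%, 4.2% and 3.7%. Under reading A at equal SEs the same freedom gives only about 0.9–1.1% two-sided.

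**The case against.** The best defence is that the authors loosely meant reading C, which is valid. The clause does name the variable, both groups and a between-group comparison, so it would be wrong to infer that the plan has no contrast at all. What is absent is the form of the estimate and the rule for success. That part of the defence stands, but the text does not choose C.

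Several stronger readings are tempting and are not supported:

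- **That the planned analysis is simply too strict.** That holds only under non-overlap, and the plan never mentions overlap.
- **That the plan both loses power and inflates false positives.** These belong to different readings. The 7.5–9.1% day-choice error presupposes a direct 5% test. Under non-overlap at equal SEs the error stays well below 5%.
- **That days 4 and 5 are certainly both eligible.** The plan does not say whether enrolment is day 0 or day 1. If it is day 0, five daily values end at day 4. Day 4 is also the only post-therapy assessment day that the Research Design section names, so it is a natural candidate. Still, it is not tied to PF ratio, and day 14 remains on the schedule where applicable.
- **That controls have no planned baseline.** The analysis section does provide for change from baseline in both groups. Only the control group's baseline day is undefined.

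**Conclusion.** The point stands as a gap in specification that should be closed before analysis. It does not show that the planned analysis is invalid. The primary clause leaves the between-group estimate, the success rule and the PF day unstated, and either literal comparison of two separate intervals does worse than one interval for the difference.

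In size: under non-overlap, two-sided alpha is about 0.6% and power about 51% against an assumed 80% at equal SEs, or about 45–50% with t-based CIs at assumed group sizes of 10 to 40. Under the rule that looks at each group against zero, false claims reach 25% at equal SEs when shared improvement is about 1.96 SE. Under a CI for the difference there is no loss, apart from an error of about 7.5–9.1% if one of two days can be chosen freely, at assumed correlations of 0.85–0.5.

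All of these rest on normal or t-based theory and on assumed SE ratios, group sizes and correlations. They show how far the readings diverge and do not predict this study's operating characteristics.

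**What to change.** Replace the primary clause with wording such as:

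> *The primary analysis estimates the treatment-minus-control difference in mean PF-ratio change between baseline and one named post-therapy day (for example day 4), with the baseline day defined the same way in both groups, and gives a single 95% CI. Improvement relative to control is concluded only if this CI lies wholly above zero. Within-group changes and other days are descriptive.*

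Use the same between-group difference for static compliance and PEEP, stating for each which direction counts as favourable. State the origin of the day count in terms that fit a non-randomized study, and align the outcome wording in Research Design with the new clause.

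The cost is a reworded paragraph, a baseline-day definition for controls and slightly more analysis work. No extra patients or measurements are needed. The real concession is commitment to one day in advance. The change does not address confounding between non-randomized groups, which needs separate treatment.

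### Mortality, a yes/no outcome, is assigned an unpaired t-test, and no method for proportions is named; in small, unequal groups neither form of the t-test gives dependable uncertainty for a proportion.

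*Combined protocol and SAP*

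**What the plan says.** Primary Statistical Plan and Analysis groups the remaining secondary endpoints in one sentence. It opens with "The study is not powered to determine additional secondary endpoints such as mortality and length of hospitalization". The words that tie mortality to the test are "mortality and length of hospitalization, but values will be collected and analyzed as unpaired t-test", and the threshold follows: the endpoints are to be "analyzed as unpaired t-test with significant p-value < 0.05". The plan does not say whether variances are pooled (Student) or kept separate (Welch).

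Research Design ends its list of secondary outcomes with "secondary bacterial infections, and mortality". Infection has no analysis method of its own. The phrase introducing mortality and length of stay presents them as examples, so infection appears to fall under the same t-test.

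A confidence interval is planned elsewhere: the primary outcome is to be assessed as "change in PF ratio from baseline for both the treatment and control groups with comparison of 95% CI between groups", with compliance and PEEP handled similarly. None is planned for mortality.

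On group sizes, Research Design says only "A second standard of care patient population is to be collected as a case control group for comparison". There is no sample size, no ratio and no expected death rate.

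**The concern.** A t-test compares means and estimates the variance separately from the mean. For a 0/1 outcome the variance is p(1 − p), so it is fixed by the event rate. If two groups have different death rates, their variances generally differ too, and the pooled test's equal-variance assumption fails. Unequal group sizes turn that failure into a standard error that is too small or too large. Welch's form drops the equal-variance assumption, but it relies on a separate variance estimate from each group. That estimate is poor when events are few, and zero when there are none.

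At stake is what readers take from the hardest clinical outcome in a ventilated population. In an unpowered comparison, the useful result is an estimated difference with honest uncertainty. The plan supplies a significance threshold and a test designed for means.

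**Working it through.** **Inputs.** From the documents: unpaired t-test, threshold 0.05, separately collected control group. Assumed, because the documents are silent: two-sided testing, independent binomial outcomes, group sizes and death rates. The plan has no figure of its own to reproduce.

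**Formulas for 0/1 data.** Each group's sample variance is s² = n·p̂(1 − p̂)/(n − 1), with expectation p(1 − p).

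- Pooled standard error: √[s_p²(1/n₁ + 1/n₂)], where s_p² = [(n₁ − 1)s₁² + (n₂ − 1)s₂²]/(n₁ + n₂ − 2).
- True standard error of the risk difference: √[p₁(1 − p₁)/n₁ + p₂(1 − p₂)/n₂].

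**Mechanism, 10 v 20 patients, expected variances inserted.**

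- Risks 50% v 10%: s_p² = (9 × 0.25 + 19 × 0.09)/28 = 0.1414. Pooled SE = √(0.1414 × 0.15) = 0.146. True SE = √(0.025 + 0.0045) = 0.172. Ratio 0.85: too small.
- Risks 10% v 50%: s_p² = (9 × 0.09 + 19 × 0.25)/28 = 0.1986. Pooled SE = √(0.1986 × 0.15) = 0.173. True SE = √(0.009 + 0.0125) = 0.147. Ratio 1.18: too large.
- Risks 50% v 30%: s_p² = (9 × 0.25 + 19 × 0.21)/28 = 0.2229. Pooled SE = √(0.2229 × 0.15) = 0.183. True SE = √(0.025 + 0.0105) = 0.188. Ratio 0.97: nearly right.

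**Exact coverage of nominal 95% intervals.** For every pair of death counts, multiply the two binomial probabilities, then add up those pairs whose interval contains the true difference. Each cell gives pooled / Welch / Newcombe, in percent. The smaller group's risk is listed first.

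| True risks | 10 v 20 | 10 v 30 | 15 v 45 |
|---|---|---|---|
| 50% v 10% | 89.1 / 94.6 / 95.8 | 87.3 / 94.5 / 95.4 | 85.4 / 94.7 / 94.8 |
| 10% v 50% | 98.2 / 93.8 / 95.8 | 98.9 / 92.8 / 94.5 | 98.8 / 92.8 / 95.0 |
| 50% v 30% | 93.6 / 94.3 / 95.2 | 93.8 / 94.3 / 94.9 | 93.8 / 94.3 / 94.9 |
| 30% v 50% | 95.7 / 94.3 / 94.5 | 96.1 / 93.7 / 94.7 | 96.1 / 94.3 / 94.8 |
| 10% v 10% | 96.3 / 95.1 / 98.6 | 97.2 / 87.5 / 97.2 | 96.5 / 85.8 / 96.7 |

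Pooled coverage fails in the first two rows. Welch mends those but fails in the last row. Newcombe does not fall materially below 95% in any row, and is conservative at low rates.

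**Type I error, equal death rates.** Over rates of 5% to 50% and seven pairs of sizes from 10 v 10 to 15 v 45, the pooled t-test rejects in 0.1% to 5.5% of trials. Welch at 10% in both groups rejects in 12.5% at 10 v 30 (100 − 87.5) and 14.2% at 15 v 45 (100 − 85.8).

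**Undefined result.** With no deaths in either group the t statistic is 0/0. The probability is (1 − p)^(n₁ + n₂). At 10% mortality this is 0.9²⁰ = 0.12 for 10 v 10, 0.9³⁰ = 0.042 for 10 v 20 and 0.9⁴⁰ = 0.015 for 10 v 30. At 30% it is 0.7²⁰ = 0.0008 for 10 v 10.

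**The case against.** The strongest reply is that the plan specifies only a p-value. It names neither pooled variance nor an interval for mortality, so poor coverage describes something that was not planned. This stands against the reading that the trial will publish a misleading mortality interval or too many false positives: under the usual pooled form, the planned p-value is not inflated. It does not rescue the plan. The form is left open, Welch does inflate that p-value in some settings, and a bare p-value from an unpowered comparison tells readers little.

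Second, the worst coverage needs unequal groups and a 40-point risk gap. This also stands. At 50% v 30% or the reverse, the error is at most about 1.4 points. With equal groups, even 50% v 10% gives 95.2% (10 v 10), 93.8% (20 v 20) and 94.3% (30 v 30). Imbalance is possible under this design, but the documents do not establish it.

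Third, a reader might infer that the test breaks down whenever a group has no deaths. It does not: a zero in one group alone still gives a pooled result. Zero deaths in both groups is unlikely in mechanically ventilated patients with ARDS.

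Fourth, contrasts between the t-test and Fisher's test prove less than they seem to. For 0/10 v 4/10 deaths, pooled t gives p = 0.025 and Fisher p = 0.087. But the Newcombe interval is about −69% to −4%, which excludes zero, and the Barnard and Boschloo exact tests both give p = 0.042. Much of that gap is Fisher's conservatism.

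**Conclusion.** The concern holds in limited form. The plan names an unsuitable test for mortality, apparently also for secondary bacterial infection, and nothing elsewhere corrects it. That infection will be recorded as yes/no is an inference.

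Under assumed small, unequal groups, pooled-interval coverage runs from 85% to 99% depending on the risks and on which group is smaller. It is close to nominal for moderate differences at mid-range rates. Welch is not a safe substitute at low event rates. All these figures rest on assumed sizes and rates.

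The documents do not support saying that the planned mortality p-value is inflated under the pooled form, that group sizes will be unequal, or that the analysis is likely to be incomputable. Severity is minor to moderate: mortality is a declared unpowered secondary endpoint, and a better method leaves the comparison unpowered and unadjusted for confounding.

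**What to change.** Remove mortality from the t-test sentence. For mortality and secondary bacterial infection, report counts by group and the risk difference with a Newcombe or Miettinen-Nurminen 95% interval as the main result.

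If a p-value is wanted, use one consistent with that interval (a score or unconditional exact test). Otherwise use Fisher's exact test and state that it is conservative and may disagree with the interval.

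Naming the Welch form for the continuous duration endpoints is an optional, minor clarification.

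The cost is one sentence in the statistics section, with no new data and no change to patient care. The downside is that some borderline differences may no longer be called significant.

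### Secondary endpoints the study is not powered for each carry a p < 0.05 significance rule, with no multiplicity control and no exploratory label

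*Combined protocol and SAP*

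**What the plan says.** The Research Design section names change in PaO₂/FiO₂ as the primary outcome. Its secondary outcomes are change in static lung compliance and then "duration of mechanical ventilation, length of ICU stay, length of hospitalization, secondary bacterial infections, and mortality".

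The Primary Statistical Plan and Analysis section treats the outcomes in four ways:

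- **Primary outcome:** "change in PF ratio from baseline for both the treatment and control groups with comparison of 95% CI between groups".
- **Compliance and PEEP:** "Secondary endpoints of change in static lung compliance and change in PEEP will be analyzed in a similar fashion to change in PF ratio". No p-value rule is attached.
- **Additional secondary endpoints:** "The study is not powered to determine additional secondary endpoints such as mortality and length of hospitalization", but in the same sentence their "values will be collected and analyzed as unpaired t-test with significant p-value < 0.05".
- **MPO-DNA in lavage fluid:** this "will be compared before and after therapy with paired t-test analysis with significant p-value < 0.05".

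The document gives no sample size, effect size, SD, event rate, family-wise error rate, testing hierarchy or exploratory label. The control group is not randomized: "A second standard of care patient population is to be collected as a case control group for comparison".

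**The concern.** One sentence both disclaims power for a set of endpoints and tells the analyst when to call them significant. The disclaimer warns the reader not to over-read a null result. It does nothing to restrain a positive one. A report that followed the plan exactly could describe dornase alfa as significantly better or worse on mortality, ventilator days or length of stay on the strength of one unadjusted p-value among several.

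Two things follow. The chance that at least one endpoint crosses the threshold when nothing differs is above the nominal 5%. And where power is low, the estimates that do cross are on average larger than the truth. The problem lies in the decision rule, whichever test is used for each outcome.

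**Working it through.** **Inputs.** From the plan: a threshold of 0.05 per test. Two-sided testing is assumed, since sidedness is not stated. The number of endpoints is read as five: ventilation duration, ICU stay, hospital stay, secondary bacterial infection and mortality. The analysis section names only two of these, as examples, but gives the other three no other analysis. The plan states no power or family-wise error figure, so there is none to reproduce.

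**Step 1: chance of at least one false positive, no true effect.** For k independent tests this is 1 − 0.95^k.

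- k = 5: 1 − 0.95^5 = 1 − 0.774 = 0.226, or 22.6%.

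The three durations overlap, so independence gives a high figure. Simulation with correlated normal test statistics (at least 400,000 draws per case) gives:

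| Assumed correlation | At least one p < 0.05 among five |
|---|---|
| None | 22.6% |
| Durations 0.3, all others 0.2 | about 21% |
| Durations 0.8, all others 0.2 | about 18% |
| All pairs 0.5 | 18.3% |
| All pairs 0.7 | 14.9% |
| All pairs 0.9 | 10.1% |

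The range is therefore about 10% to 23%, or two to four and a half times the nominal 5%.

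**Step 2: smallest difference that can reach p < 0.05.** With n per group and equal groups (assumed), an observed difference must exceed t(0.975, 2n − 2) × √(2/n) sample SDs:

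- n = 10: 2.101 × 0.447 = 0.94 SD
- n = 15: 2.048 × 0.365 = 0.75 SD
- n = 30: 2.002 × 0.258 = 0.52 SD

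**Step 3: average inflation of estimates that pass.** This is the mean absolute estimate among results with p < 0.05, divided by the true effect. It was obtained by simulating two-sample t-tests (at least 40,000 per cell). Group sizes and effects are assumptions, chosen to show the range.

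| True effect | n per group | Average inflation |
|---|---|---|
| 0.2 SD | 10 | 5.1 |
| 0.2 SD | 15 | 4.3 |
| 0.2 SD | 30 | 3.1 |
| 0.3 SD | 50 | 1.7 |
| 0.3 SD | 100 | 1.3 |
| 0.5 SD | 10 | 2.2 |
| 0.5 SD | 30 | 1.4 |
| 0.5 SD | 50 | 1.2 |
| 0.8 SD | 10 | 1.5 |
| 0.8 SD | 30 | 1.08 |

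At 0.2 SD, power is 7%, 8% and 12% for 10, 15 and 30 per group. About 12%, 8% and 3% of the significant estimates have the wrong sign. In the listed 0.5 SD and 0.8 SD cells the wrong-sign share is below 1%.

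**Step 4: would a multiplicity correction be enough?** Bonferroni over five tests uses 0.05/5 = 0.01 each, with a family-wise error of 1 − 0.99^5 = 4.9% if independent. That deals with Step 1. It makes Step 3 worse, because a stricter threshold lets through only larger estimates.

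**The case against.** The other side has a fair case. The plan has one primary hypothesis and one primary outcome, and it discloses the lack of power in the same sentence as the threshold. Nowhere does it say that a secondary result would support an efficacy claim. Leaving secondary endpoints unadjusted is common in a small single-center study. What is missing could be seen as little more than a label.

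Most of that stands, and it limits the weight of the point. It does not remove it: the sentence states a rule for calling results significant, and nothing else in the document qualifies that rule.

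A reader might also infer more than the documents support:

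- *That a chance finding is likely.* At 22.6% or less, no false positive is the more probable outcome by more than 3 to 1 (0.774 against 0.226). Independent tests would have to number 14 before the chance passed one half (51.2%).
- *That any significant estimate will be greatly exaggerated.* Inflation is an average, not a property of every estimate. Its size cannot be fixed without a sample size and an effect. Not being powered means not sized for these endpoints; it does not show that power is close to nil.
- *That the plan declares these endpoints significant.* It sets a threshold and declares nothing.
- *That MPO-DNA belongs in the same family.* It is a paired, within-patient mechanistic test serving Aim #2, not one of the between-group clinical endpoints.
- *That compliance and PEEP should be tested only after a positive PF result.* Both fall outside the p-value rule, and Aim #1 names compliance alongside PaO₂/FiO₂.

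**Conclusion.** The point holds in this form: the plan keeps a 0.05 significance rule for endpoints it says it is not powered for, without multiplicity control or an exploratory label. The chance of at least one false significant result among five is 22.6% at most, about 18% to 21% under moderate correlation, and about 10% under very strong correlation. Estimates that pass are inflated on average, by about 5 times to about 1.1 times across the assumed group sizes and effects.

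These figures rest on a count of five, two-sided tests, equal groups, valid tests and no confounding. With a non-randomized control group, confounding could raise the actual error. Neither a correction for multiplicity nor a change of label would repair that. Since these are secondary endpoints and the lack of power is disclosed, this is a cheap improvement worth making, not a flaw in the primary analysis.

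**What to change.** In the Primary Statistical Plan and Analysis section, remove the significance threshold for the additional secondary endpoints and replace it with text along these lines:

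> Duration of ventilation, ICU stay, hospital stay, secondary bacterial infection and mortality will be reported as between-group differences with 95% CIs. They are exploratory and no claim of statistical significance will be made for them. The efficacy conclusion rests on the PF ratio.

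Listing the five by name also settles which endpoints the rule covers. Leave the compliance and PEEP analyses as planned. Identify the paired MPO-DNA test as the separate mechanistic test for Aim #2.

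This is preferable to Bonferroni, which would control false positives but increase the inflation of whatever passed. It also matches the interval-based reporting already planned for the PF ratio, compliance and PEEP.

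The cost is a wording change: no extra patients, data or procedures. The sponsor gives up the option of calling an isolated secondary result significant.

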Study Title: Dornase Alfa for ARDS in Patients
with SARS-CoV-2

NCT number: 04402970

Document Date: Last approved/updated
3/08/2021

Background and Significance

Health care systems across the world are being inundated with patients who are critically ill due to infection with Severe Acute Respiratory Syndrome-Coronavirus-2 (SARS-CoV-2) causing Coronavirus Disease 2019 (COVID-19). Around 10% of those infected will develop the most severe manifestation of the disease requiring admission to an intensive care unit¹. Early reports suggested neutrophil extracellular traps (NETs) as being a potential contributor to the severity of disease in some patients with COVID-19². The primary innate immune role for NETs is to trap and kill invading microbes, but in severe cases of COVID-19, NETs appear to cause significant morbidity in the lungs with associated microthrombi formation, endothelial damage, capillaritis, neutrophilic mucositis and mucus accumulation³⁻⁶. Plasma levels of NET activity are increased in patients who requiring intubation and are inversely correlated with arterial blood oxygen content to fraction of inspired oxygen ratio ($\text{PaO}_2/\text{FiO}_2$)⁷. Dornase alfa, currently is in use in patients with Cystic Fibrosis, works by degrading large extracellular DNA in the airways^{8,9}. We proposed a trial of using inhaled dornase alfa as a therapeutic target to reduce excess NETs in patients with acute respiratory distress syndrome (ARDS) secondary to COVID-19 pneumonia, with outcome aims including improved lung compliance and gas exchange¹⁰.

Aims and Objectives

Aim #1: Determine if use of nebulized dornase alfa in ARDS secondary to COVID-19 will lead to improved pulmonary mechanics as measured by surrogate values of $\text{PaO}_2/\text{FiO}_2$ and static lung compliance.

Aim #2: Determine if use of nebulized dornase alfa in ARDS secondary to COVID-19 will lead to a reduction in alveolar and serum NET activity.

Research Design

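### Aim 2 asks whether dornase alfa lowers NET activity, but the only NET test stated is an uncontrolled before-and-after comparison, which cannot attribute a change to the drug

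*Combined protocol and SAP*

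**What the plan says.** Aims and Objectives gives two aims. The second is to determine whether nebulized dornase alfa "will lead to a reduction in alveolar and serum NET activity".

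Research Design describes the study in these terms: "A single center, non-randomized, controlled before-and-after clinical study was designed". It adds a comparison group: "A second standard of care patient population is to be collected as a case control group for comparison". The sampling is set out as one sequence: consent, blood and lavage, three days of dornase alfa, and then on day 4 "blood samples and BAL fluid samples will again be collected to determine change in serum and alveolar NET activity". Nothing is said about sampling in the control group.

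Primary Statistical Plan and Analysis compares the change in PF ratio between the treatment and control groups by 95% CI, and treats static compliance and PEEP the same way. For NETs it states one test: "Bronchoalveolar fluid analysis for MPO-DNA will be compared before and after therapy with paired t-test analysis with significant p-value < 0.05". It states no test for serum NET activity and no rule that turns a p-value into a conclusion on Aim 2.

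**The concern.** Aim 2 is a causal question. A paired test on treated patients estimates the drug effect plus everything else that changes between the baseline sample and day 4: the course of the illness, co-treatment, regression to the mean, and loss of patients before the second lavage. It has no means of separating these.

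The error can go either way. A significant fall could be taken as a dornase effect when an inert drug would have shown the same fall. A null result could hide a real effect offset by worsening disease. Since this is the only NET test offered, the plan as written has no analysis that can answer its second aim. The serum half of the aim has no stated analysis at all.

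**Working it through.** **Question against analysis.**

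| Item | Where | Comparison with controls? |
|---|---|---|
| PF ratio | Primary Statistical Plan and Analysis | Yes, change by group with 95% CI |
| Static compliance, PEEP | same section | Yes, analysed like PF ratio |
| BAL MPO-DNA | same section | None named; paired t-test only |
| Serum NET activity | Aims and Objectives; Research Design | No test stated |

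The plan does not say that MPO-DNA is its measure of NET activity, but it names no other assay or NET test. The mismatch with Aim 2 follows from this reading alone and needs no arithmetic.

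**Illustration of the mechanism.** The plan has no figure to reproduce: no n, SD, effect size or time course for MPO-DNA. Every input below is assumed: 10 or 20 patients per group; normal changes with equal SD in both groups; effects in SDs of the within-patient change; two-sided 0.05 (the plan does not state sidedness), counting only significant results in the direction of a reduction.

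Formulas:
- Paired: P(T > t(0.975, n−1)), with T noncentral t and noncentrality d√n.
- Two groups, change compared: P(T > t(0.975, 2n−2)), noncentrality δ√(n/2), where δ is the between-group difference in mean change.

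*Inert drug, natural fall d, paired test.* Example: n = 10, d = 0.3 gives noncentrality 0.3 × √10 = 0.949 and critical value 2.262, so the probability is 0.134.

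| d | 0 | 0.1 | 0.2 | 0.3 | 0.5 |
|---|---|---|---|---|---|
| 10 pairs | 0.025 | 0.047 | 0.082 | 0.134 | 0.293 |
| 20 pairs | 0.025 | 0.062 | 0.133 | 0.246 | 0.564 |

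*Inert drug, two-group comparison of change.* If both groups share the same natural fall, δ = 0 and the rate is 0.025 whatever the fall. If their natural courses differ by 0.2 SD, noncentrality is 0.2 × √5 = 0.447 (10 per group) or 0.2 × √10 = 0.632 (20 per group), and the rates are 0.062 and 0.090. A non-randomized comparison therefore removes shared drift only.

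*Masking, paired test, true reduction 0.6 SD.* A natural rise of 0.3 SD leaves a net fall of 0.6 − 0.3 = 0.3 SD. Power drops from 0.396 to 0.134 with 10 pairs and from 0.721 to 0.246 with 20.

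*Power cost of the two-group comparison, true reduction 0.6 SD, no drift.* 0.245 against 0.396 for the paired test (10 per group); 0.456 against 0.721 (20 per group).

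**The case against.** The strongest reply is that the paired test may simply follow from the data available. PF ratio, compliance and PEEP are to be measured daily, whereas lavage MPO-DNA is not. Sampling is described only for patients who go on to receive dornase alfa, and the controls are standard-of-care patients who may have had no research bronchoscopy. This stands. A reader might infer from the contrast with PF ratio that a control comparison was available and left unused; the documents do not support that, because they do not say whether controls are sampled.

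A reader might also infer that the plan itself shows that lavage NETs drift. It does not. The background says: "Plasma levels of NET activity are increased in patients who requiring intubation and are inversely correlated with arterial blood oxygen content". That is a plasma association with no time course. The rule that begins "Therapy will be discontinued in any patients who develop treatment failure" concerns oxygen need, compliance and rescue therapy, not NETs. The point rests on the general logic that an uncontrolled change cannot be attributed, not on evidence of drift.

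Nor do the documents settle whether a between-group analysis should use change scores or adjust for baseline. That depends on whether a baseline difference between the groups would persist or regress to a common mean, which is not stated.

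Three further replies are fair. Aim 1 is worded just as causally, and even a control comparison here is non-randomized. The recording of co-treatment ("Clinical study information will include age, sex, co-morbidities, therapies received") feeds no stated analysis of any endpoint, so that gap is not peculiar to NETs. And NET activity is not among the listed primary or secondary outcomes. These limit the reach of the point, but Aim 1 at least has a control comparison for its measures and Aim 2 has none.

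**Conclusion.** The point holds, confined to Aim 2: the only NET test stated cannot answer the causal question the aim asks, and serum NET activity has no stated test. This rests on the text alone. It is more than missing detail, because following the plan exactly would still leave the aim unanswered. It should be corrected.

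The size is unknown. The illustrative rates (for example 13% to 25% at a 0.3 SD natural fall, against 2.5%) rest wholly on assumed n and drift, and are not findings about this trial.

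It would go too far to conclude that the primary outcome or the listed secondary outcomes are compromised by this; they do not depend on the NET test. Nor does the plan claim that p < 0.05 proves a drug effect. The risk is that such a result, read beside the wording of Aim 2, is taken that way.

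**What to change.** 1. State whether controls have baseline and day-4 blood or lavage samples.
2. If they do, compare change in NET activity between groups with a 95% CI, in line with the PF-ratio analysis, and report it as a non-randomized association.
3. If they do not, add no procedure. Keep the paired test, and restate Aim 2 and its conclusion as within-patient change in NET activity during treatment, not attributable to dornase alone.
4. Apply the same analysis to the serum samples already planned.

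Cost: wording in the aim and the statistical section, and a more modest claim. Under option 2 there is also lower power than the paired test for the same true effect, and the assay of any control samples that exist but were not already due to be assayed. No new sampling is needed under either option.
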